1.8.5 Patient-Reported Outcomes

Quality of Life (QOL). The Functional Assessment of Cancer Therapy-Head and Neck Symptom Index (FACT-H&N SI) will be used to measure global quality of life and functional decline from the patient's perspective. The FACT-H&N SI is an internationally validated QOL tool. It is a multidimensional, patient-self report QOL instrument that has been specifically designed and validated for this patient population.⁴⁶ The questionnaire consists of 10 core items that assess patient function in 4 domains: Physical, Social/Family, Emotional, and Functional well-being. Each item is rated on a 0 to 4 Likert type scale, and then combined to produce subscale scores for each domain, as well as a global QOL score; higher scores represent better QOL. The FACT-H&N SI can be completed by the patient in about 5 minutes, is available in 26 languages, and will be completed at baseline, end of cycle 2, and end of cycle 6. See Appendix A for FACT-H&N-SI.

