5.4 Duration of Treatment and Follow-up

5.4.1 Treatment Duration:

Treatment will continue until one of the following criteria applies:

- Disease progression,
- Intercurrent illness that prevents further administration of treatment,
- Unacceptable adverse event(s),
- Patient elects to withdraw from the study for any reason,
- General or specific changes in the patient's condition render the patient unacceptable for further treatment in the judgment of the investigator, including pregnancy.
- March 31, 2021 (expiration date of ficlatuzumab)

5.4.2 Follow up duration - WITHOUT progressive disease:

Patients who stop treatment **without** progressive disease will be followed approximately every 8 weeks (+/- 2 weeks) until progression of disease, then every 12 weeks (+/- 2 weeks) for 2 years after disease progression. Patients who begin a new line of therapy will be censored for progression and be followed per the progressive disease schedule. Refer to Section 8.5 for post-treatment protocol-required evaluations.

5.4.3 Follow up duration - WITH progressive disease:

Patients who stop treatment **with** progressive disease will be followed for survival every 12 weeks (+/- 2 weeks) for two years after disease progression, or until death, whichever occurs first. Refer to Section 8.5 for post-treatment protocol-required evaluations.

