8.3 Evaluations during study treatment

8.3.1 Every Two Weeks – Day 1 and Day 15 of each cycle (+/- 3 days)

Note: The following may be performed on the day of or within the 3 days prior to study drug administration. If the subject is deemed not acceptable for drug administration, refer to the visit delay and skipped visit description in Section 5.5. Subjects can return within the +3-day window, in 1 week, or for the next regularly scheduled treatment. If appropriate, the visit can be skipped and treatment can occur on schedule with the next regularly scheduled treatment (i.e., 2 weeks later).

- Physical examination, including vital signs, weight and ECOG performance status
- Adverse Event/Toxicity assessment with attribution
- Update of concomitant medications
- Complete blood count, including platelets and differential
- Blood chemistries:
 - o BUN, creatinine, electrolytes (K⁺, Na⁺, Cl⁻, CO₂), glucose, calcium, magnesium
 - Note: Refer to Table 4B regarding grading, repletion, holding treatment, and/or dose reductions.
- Liver function tests:
 - o total protein, albumin, total bilirubin, AST (SGOT), ALT (SGPT), and alkaline phosphatase
- Study drug administration
 - o For both agents: Recalculate the doses of both ficiatuzumab and cetuximab only if there is a ≥ 10% change in weight. Exception: If, in the opinion of the treating investigator, weight change of ≥ 10% is due to edema, recalculation of the ficiatuzumab dose is not required. This decision must be clearly documented.

8.3.2 Every 8 Weeks (the end of even cycles – "Day 28"/8 weeks, 16 weeks, etc.)

- Quality of life assessment (FACT-H&N) end of cycle 2 and cycle 6 only.
 - The FACT-H&N may be done cycle 3, day 1/cycle 7, day 1 for subjects who remain on treatment.
 - If a subject stops treatment per the cycle 2 or cycle 6 scan, the FACT-H&N scheduled for C2D28 or C6D28 can be done at the End of Treatment visit.

- Tumor measurements according to RECIST 1.1 may be done during the last week of an even cycle, by CT scan or MRI.
 - Tumor measurements must be performed every 8 weeks, +/- 7 days for (at least) the first 12 cycles. (See Section 8.3.3 regarding an optional tumor measurements schedule for subjects on treatment longer than 12 cycles.)
 - The schedule is independent of any treatment delays within the 2 cycles since the prior response assessment. (See Section 5.5.1 regarding missed and/or skipped visits.)

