8.4 End-of-treatment (EOT) evaluations

- Patients who discontinue treatment for any reason will have an evaluation with the
 following tests, if possible unless performed within the previous 2 weeks (except as
 noted below) and unless otherwise indicated below. The EOT evaluations should be
 performed as soon as possible but within 30 days after the **off-treatment decision**date.
- Physical examination, including vital signs, weight and ECOG performance status
- Adverse Event/Toxicity assessment with attribution
- Update of concomitant medications
- Complete blood count, including platelets and differential
- Blood chemistries:
 - o BUN, creatinine, electrolytes (K⁺, Na⁺, Cl⁻, CO₂), glucose, calcium, magnesium
- Liver function tests:
 - Total protein, albumin, total bilirubin, AST (SGOT), ALT (SGPT), and alkaline phosphatase
- Research blood for correlative studies
- For subjects that end treatment at C2D28 or C6D28, Quality of life (QoL) assessment (FACT-H&N)
 - Subjects that end treatment after C4D28 but prior to C6D28 due to expiration of the study drug will complete the QoL assessment at the EOT visit
- Tumor measurements according to RECIST 1.1 (unless performed within the previous
 28 days if it is an appropriate standard of care procedure the EOT tumor
 measurement will not be performed only for the research)

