10.5.1 Patient-Reported Outcomes

Quality of life will be described according to FACT-H&N Symptom Index scores obtained at baseline and after two cycles of study treatment.

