- ⁹ A negative pregnancy test is required in women of child-bearing potential within 14 days prior to registration. Negative pregnancy test must be confirmed again within 3 days prior to first drug administration.
- ¹⁰ Archived tumor tissue, preferably the most recent tissue available, may be substituted if the biopsy is not safe and/or feasible, and/or would present unacceptable clinical risk, and the Sponsor has approved omission of the baseline biopsy. See Section 9.2.
- ¹¹ Archived tissue, preferably primary tumor tissue blocks (or slides, if blocks are not available) from procedures **prior to clinical cetuximab exposure.** This is not an eligibility requirement and subjects can be randomized without this confirmation.
- ¹² For scheduling convenience, tumor measurements may occur on day 1 of the following cycle, so long as the scan is done and results are known **prior** to drug administration.
- ¹³ Tumor measurements must be performed every 8 weeks, +/- 7 days, regardless of any delay that occurs within the prior 2 cycles. Subjects who remain on treatment past Cycle 12 can transition to tumor assessments being performed every 12 weeks, +/- 14 days. Refer to Section 8.3.3.
- ¹⁴ FACT-H&N Symptom Index will be performed at baseline and at the end of cycle 2 and cycle 6 only, or when the subject is censored for progression after C4D28 but before C6D28 (see EOT procedures). For scheduling convenience, FACT-H&N Symptom Index may be completed on day 1 of the following cycle or at the EOT visit.
- ¹⁵ For oropharyngeal & unknown primary, p16 status must be established, if not previously known, before randomization.
- ¹⁶ Subject will be followed for AEs/SAEs for 60 days **after last dose of study drug** or until the initiation of subsequent antineoplastic therapy, whichever is earlier. (Refer to protocol Section 8.5.1 for important and specific details on collection and follow up of AEs.)
- ¹⁷ Subjects who end treatment **due to a reason other than progressive disease** will have an AE assessment at the first follow-up visit. (Refer to protocol Section 8.5.1 for important and specific details on collection and follow up of AEs.)
- ¹⁸ Subjects who end treatment **due to progressive disease** will have an AE assessment at least 60 days after last dose of study drug. (Refer to protocol Section 8.5.1 for important and specific details on collection and follow up of AEs.)

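### The end-of-treatment quality-of-life form is limited to certain stopping times, so patients who stop before the end of cycle 2 have no post-baseline score, and Section 10.5.1 plans neither for their absence nor for the cycle 6 forms

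*Combined protocol and SAP*

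**What the plan says.** Describing patient-reported quality of life is an exploratory objective (Section 2.3). Section 1.8.5 says the FACT-H&N Symptom Index measures global quality of life and functional decline, and that it "will be completed at baseline, end of cycle 2, and end of cycle 6". Section 8.3.2 agrees: "Quality of life assessment (FACT-H&N) end of cycle 2 and cycle 6 only". It also lets a patient who stops on the cycle 2 or cycle 6 scan complete that form at the end-of-treatment (EOT) visit.

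The EOT visit in Section 8.4 covers discontinuation for any reason. Examination, adverse events, laboratory tests and research blood are asked of all these patients where possible, unless recently done. The quality-of-life form is tied to when treatment stops: "For subjects that end treatment at C2D28 or C6D28, Quality of life (QoL) assessment". One exception is added: "Subjects that end treatment after C4D28 but prior to C6D28 due to expiration of the study drug will complete the QoL assessment".

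Footnote 14 of the Study Calendar (Appendix C) words that exception differently: "or when the subject is censored for progression after C4D28 but before C6D28". Drug expiry is one route to such censoring (Section 5.1). Another is in Section 5.4.2: "Patients who begin a new line of therapy will be censored for progression and be followed per the progressive disease schedule". The calendar shows no quality-of-life form in either follow-up phase.

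Section 10.5.1 describes scores "obtained at baseline and after two cycles of study treatment". Neither it nor Section 10.6 says how missing quality-of-life data will be handled.

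**The concern.** Whether a form exists depends on when and why a patient stopped. Stops before C2D28 for toxicity, intercurrent illness or symptomatic deterioration leave only a baseline score, and no later visit recovers one. These are patients in whom decline is most likely. Section 6 defines symptomatic deterioration as a global worsening of health that forces treatment to stop without objective progression.

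Later exits are also covered unevenly. Under Section 8.4, a patient stopped between C4D28 and C6D28 by lot expiry completes the form, while one stopping in the same weeks for progression does not. What is at stake is how faithfully the exploratory description reflects patients' experience. Separately, cycle 6 and expiry-exit forms are collected with no stated use.

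**Working it through.** **1. Coverage by time of stopping** (Sections 8.3.2, 8.4 and 10.5.1; Appendix C)

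| Treatment stops | Cycle 2 form | Exit form | In the 10.5.1 summary |
|---|---|---|---|
| Before C2D28 | No | No | No |
| At C2D28, any reason | Yes (may be done at EOT) | Same form | Yes |
| After C2D28, up to and including the C4D28 scan | Yes | No | Yes |
| C4D28 to C6D28, drug expiry | Yes | Yes | Yes (cycle 2 score only) |
| C4D28 to C6D28, new therapy without progression | Yes | No under 8.4; possibly under footnote 14 | Yes (cycle 2 score only) |
| C4D28 to C6D28, progression | Yes | No | Yes (cycle 2 score only) |
| At C6D28, any reason | Yes | Yes | Yes (cycle 2 score only) |

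Only the first row is lost from the planned summary.

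**2. Reproducing the plan's figure.** Inputs are median PFS of 2 and 3.33 months and 33 eligible patients per arm (Section 10.3). With exponential PFS, S(t) = 0.5^(t/median), and 4.348 weeks per month, 16 weeks is 3.68 months. S = 0.5^(3.68/3.33) = 0.465, which agrees with the 0.46 in Section 10.7.

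**3. PFS events by scan interval,** before any other stopping. Share = S at the previous scan minus S at this scan; count = 33 × share.

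| Median | S(8 wk) | S(16 wk) | S(24 wk) | Cycle 2 scan | Week-16 scan | Cycle 6 scan |
|---|---|---|---|---|---|---|
| 2 months | 0.529 | 0.279 | 0.148 | 47.1% (15.6) | 24.9% (8.2) | 13.2% (4.3) |
| 3.33 months | 0.682 | 0.465 | 0.317 | 31.8% (10.5) | 21.7% (7.2) | 14.8% (4.9) |

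The largest group, at the cycle 2 scan, is offered a form. The week-16 group, about 7 to 8 of 33, has no exit form. PFS events include deaths (Section 10.2), so not all of these forms could be recovered.

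**4. Stops before C2D28.** The documents give no rate, so I assume that a share m stops for reasons other than a scan before week 8. Week-8 forms = 33 × (1 − m):
- m = 10%: 29.7
- m = 20%: 26.4
- m = 30%: 23.1

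**5. Effect on the week-8 mean.** Let D be the observed patients' mean minus the mean the missing patients would have had. The full mean is (observed mean) − m × D, so the overstatement is m × D. Ten items scored 0-4 give a total of 0-40 if simply summed, with higher scores better (Section 1.8.5). For assumed D from 0 to 8 points:
- m = 10%: 0 to 0.8 points
- m = 20%: 0 to 1.6 points
- m = 30%: 0 to 2.4 points

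**6. Cycle 6 form.** With no other stopping, at most 33 × S(16 wk) = 9.2 (median 2 months) or 15.3 (median 3.33 months) patients remain to supply it. If the assumed early-stopping hazard continues to week 24, multiply by (1 − m)³:
- m = 10%: 6.7 or 11.2
- m = 20%: 4.7 or 7.9
- m = 30%: 3.2 or 5.3

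**The case against.** A reader might infer that patients who stop at the week-16 scan or for toxicity are missing from the reported quality of life, and that the report is therefore biased upward. The documents do not support that. Section 10.5.1 uses only baseline and the score after two cycles. Week-16 stoppers, and patients stopping for toxicity after cycle 2, were due that form while on treatment. Those stopping on the cycle 2 scan, the largest group in the table, are explicitly provided for, and a toxicity stop falling at C2D28 or C6D28 is covered too. The week-16 count therefore measures lost exit forms and does not measure loss from the planned summary.

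Nor is upward bias established. It is plausible, because sicker patients tend to leave earlier, but it is zero if D = 0, and the documents give neither m nor D. It would also be too strong to say that every toxicity stop between C4D28 and C6D28 is excluded: under footnote 14, one followed by new therapy might qualify.

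It can fairly be added that fixed-time collection is a legitimate choice for an exploratory objective in a non-comparative trial. EOT scores are also an imperfect substitute for week-8 scores, since the visit may fall up to 30 days after the off-treatment decision. Both points stand. They limit the importance of the concern and shape the remedy. They do not answer the lack of any post-baseline score for stops before C2D28, the silence on missing data, the unused cycle 6 form or the conflict between Section 8.4 and footnote 14.

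**Conclusion.** The point holds as a cheap improvement to an exploratory, descriptive objective. No PFS analysis, futility boundary or arm-selection decision depends on it.

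- **Before C2D28:** patients who stop have no post-baseline score and are absent from the 10.5.1 description. Their number is unknown. The week-8 summary probably overstates quality of life, by 0 to 2.4 points of 40 under the assumed ranges (10% to 30% stopping early, 0 to 8 points lower).
- **Between C2D28 and C6D28:** week-16-scan stoppers (about 7 to 8 of 33 per arm, assuming exponential PFS at the plan's medians) and others outside the listed exceptions have a cycle 2 form but no exit form.
- **Cycle 6:** fewer than half of an arm can supply the form even with no other stopping (at most about 9 to 15 of 33), and Section 10.5.1 plans no use for it.
- **Consistency:** Section 8.4 and footnote 14 define the C4D28 to C6D28 exception differently and must be reconciled.

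**What to change.** - **Section 8.4 and footnote 14:** collect the FACT-H&N Symptom Index at the EOT visit for every subject, whatever the reason or cycle, unless completed in the previous 2 weeks. This also removes the conflict over the exception.
- **Section 10.5.1:** describe baseline, cycle 2, cycle 6 and EOT scores by arm, with completion counts and reason for stopping. Report EOT as its own time point. Use an EOT score in place of the cycle 2 score, for stops before C2D28, only as a sensitivity analysis.
- **If collection has closed:** this is likely, since ficlatuzumab dosing was to end by March 31, 2021 and the current text is dated 05/23/2023. Apply the Section 10.5.1 change to the forms in hand, and state that each scheduled summary omits patients who stopped before that time point.

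The cost is one 10-item form of about 5 minutes at a visit that already takes place; Section 8 already allows completion by phone or another method. EOT forms will come at variable times, and some very ill patients will still not complete one.

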8.5 Post-treatment follow-up

8.5.1 Adverse Event and Concomitant Medication Follow-up

AEs and SAEs will be followed per the details below regardless of the reason the subject ended treatment.

- Subjects will be followed for AEs (including SAEs) and pregnancy for at least 60 days after last dose of study drug(s) or until the initiation of subsequent antineoplastic therapy, whichever is earlier.
- Only new AEs that are considered related to the drug and pregnancy need to be documented during the 60 days.

- Any of related AEs that are SAEs must be reported as an SAE to the sponsor.
- AEs that are determined to be related to the study drug, whether documented during treatment or during follow-up, will be followed until resolution or stabilization.
- New concomitant medications do not need to be documented.

If a subject starts any new antineoplastic therapy, collection and follow up of AEs will stop, including AEs considered related/possibly related to the study drug, but SAEs that are considered related/possibly related may require continued assessment. Contact the Sponsor-Investigator for guidance.

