12.1 Definitions

The following definitions of terms apply to this section:

Adverse event: Any untoward medical occurrence associated with the use of a drug in humans, whether or not considered drug related. The term "Adverse Event" is inclusive of SAEs.

Life-threatening adverse event or life-threatening suspected adverse reaction: An adverse event or suspected adverse reaction is considered "life-threatening" if, in the view of either the investigator or sponsor, its occurrence places the patient or subject at immediate risk of death. It does not include an adverse event or suspected adverse reaction that, had it occurred in a more severe form, might have caused death.

Serious adverse event: An adverse event is considered "serious" if it results in any of the following outcomes:

- death,
- a life-threatening adverse event,
- inpatient hospitalization or prolongation of existing hospitalization,
- a persistent or significant incapacity or substantial disruption of the ability to conduct normal life functions, or
- a congenital anomaly/birth defect.
- Important medical events that may not result in death, be life-threatening, or require
 hospitalization may be considered serious when, based upon appropriate medical
 judgment, they may jeopardize the patient or subject and may require medical or
 surgical intervention to prevent one of the outcomes listed in this definition.
- Pregnancy

Suspected adverse reaction: Any adverse event for which there is a reasonable possibility that the drug caused the adverse event. For the purposes of IND safety reporting, "reasonable possibility" means there is evidence to suggest a causal relationship between the drug and the adverse event. Suspected adverse reaction implies a lesser degree of certainty about causality than adverse reaction, which means any adverse event caused by a drug.

Unexpected adverse event or unexpected suspected adverse reaction: An adverse event or suspected adverse reaction is considered "unexpected" if it is not listed in the investigator brochure or is not listed at the specificity or severity that has been observed; or, if an

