12.2 Description of Adverse Event Reporting Procedures

Adverse events will be recorded in the adverse events record form in the UACC OnCore CRM and reviewed by the local Principal Investigator. All Adverse Events as defined in this section will be collected starting on Cycle 1, Day 1 must be recorded. AEs will be followed per the details indicated in protocol Section 8.5.1. Only AEs meeting one of the following criteria will be entered into the OnCore CRM study database:

- Any AE that is Grade 3 or higher, regardless of relationship to the study drug
- Any AE that results in submission of a Serious Adverse Event (i.e., hospitalization for a non-serious grade AE)
- Any intolerable (per the opinion of the treating investigator) Grade 2 AE
- Any Grade AE resulting in a dose reduction of ficlatuzumab or cetuximab
- Any Grade 2 laboratory or vital sign values that are deemed clinically significant by the treating investigator
- Any Grade AE in the following categories of interest:
 - o Rash
 - Diarrhea
 - o Edema, peripheral
 - o Edema, head, face and neck
 - o Hypoalbuminemia

All adverse events will be classified using either the MedDRA term or NCI Common Terminology Criteria for Adverse Events (CTCAE) version 4.0 and will address:

- Grade
- Relationship to ficiatuzumab (not related, unlikely, possible, probable, definitely)
- Relationship to cetuximab (not related, unlikely, possible, probable, definitely)

- Causality other than study drug (disease related, concomitant medication related, intercurrent illness, other)
- Date of onset
- Date of resolution
- Frequency of event (single, intermittent, continuous)
- Event outcome (resolved, ongoing, death)
- Action taken with ficlatuzumab (none, held, dose reduced, discontinued, medication given)
- Action taken with cetuximab (none, held, dose reduced, discontinued, medication given)

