12.3 Reporting of Serious Adverse Events

All Serious Adverse Events as defined in Section 12.1 will be collected starting Cycle 1, Day 1 and must be reported to the Sponsor. SAEs will be followed per the details indicated in protocol Section 8.5.1. SAEs must be reported to the IRB of Record per local procedure.

Regardless of attribution, SAEs must be reported to the sponsor and the UACC DSMB within 24 hours of notification of the event. SAEs will also be copied to the Aveo pharmacovigilance entity, Parexel. The FiclaYCetux Serious Adverse Event Report Form must be used to report SAEs and redacted, relevant medical records must be attached when available. Follow-up information that describes an increase in severity or risk must be submitted within 24 hours of notification of the information. Follow-up SAE reports must also be reported within 24 hours of notification of updated information related to the event.

The Sponsor, UACC DSMB, and/or the Aveo pharmacovigilance entity, Parexel, may contact site personnel with queries to ensure all necessary information is obtained.

SAEs must be recorded in the OnCore "SAEs" tab.

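### Sections 8.5.1, 12.2 and 12.3 give conflicting rules for a new SAE after the last dose that the site judges unrelated, so sites may capture such events differently

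*Combined protocol and SAP*

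**What the plan says.** Section 8.5.1 follows subjects for AEs, SAEs included, for at least 60 days after the last dose, or until new antineoplastic therapy if that comes first. Within that window, "Only new AEs that are considered related to the drug and pregnancy need to be documented during the 60 days". On serious events it adds: "Any of related AEs that are SAEs must be reported as an SAE to the sponsor". It does not mention unrelated SAEs.

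Section 12.1 says the term adverse event "is inclusive of SAEs". Death and inpatient hospitalization are on its list of serious outcomes, with no exception for disease progression.

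Section 12.3 says all SAEs "will be collected starting Cycle 1, Day 1 and must be reported to the Sponsor". It then refers onward: "SAEs will be followed per the details indicated in protocol" Section 8.5.1. The next paragraph sets the reporting duty: "Regardless of attribution, SAEs must be reported to the sponsor and the UACC DSMB within 24 hours of notification of the event". Neither sentence is limited to the treatment period, and 12.3 gives no end of collection.

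Section 12.2 lists what enters the study database, including "Any AE that is Grade 3 or higher, regardless of relationship to the study drug". It makes no distinction between on and off treatment, and it also refers to 8.5.1 for how AEs are followed.

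**The concern.** Two sections state a rule for the same event and the rules differ. A site that follows 8.5.1 may leave a post-treatment hospitalization it considers unrelated out of the record. A site that follows 12.3 reports the same event within 24 hours. Each can cite the protocol.

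Three things make this more than a drafting blemish:

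- **Attribution decides what is seen.** The trial is open-label (Section 10.1), so the site judges relatedness knowing the treatment. Several serious events reported with these drugs resemble complications of advanced cancer. Section 1.4 lists Grade 3 infection and thromboembolic events with the combination, and Section 1.7.1 lists sepsis and pulmonary embolus with cetuximab.
- **Later review sees only what is submitted.** The sponsor assesses the SAEs it receives for FDA reporting (Section 12.4), and the DSMB reviews the SAEs submitted to it (Sections 11.3 and 11.4).
- **The toxicity analysis has no stated end.** Section 10.4.1 starts evaluability at the first ficlatuzumab treatment and names no closing date. Post-treatment events can therefore enter the tabulation at one site and not at another.

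**Working it through.** No figure in the plan bears on this, so the check is a comparison of texts on one test case.

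**Test case.** A new hospitalization, Grade 3, on day 30 after the last dose. No new antineoplastic therapy has started, and the site judges the event unrelated.

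| Section | Limited by attribution? | Limited in time? | What it requires here |
|---|---|---|---|
| 8.5.1 | Yes, related only | 60 days, or new therapy if earlier | No documentation and no sponsor report |
| 12.2 | No, for Grade 3 or higher | Start given, no end | Database entry |
| 12.3 | No | Start given, no end | Report to sponsor and DSMB within 24 hours |

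**Step 1: does the 8.5.1 limit reach SAEs?** Yes. Section 12.1 includes SAEs in AEs, 8.5.1 names SAEs in its own follow-up sentence, and its reporting sentence is confined to related SAEs.

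**Step 2: do the cross-references settle the order of precedence?** No. Section 12.3 defers to 8.5.1 on how SAEs are followed. Its reporting duty comes after that deferral and carries no qualification. Section 12.2 defers in the same way. Study calendar footnotes 16 to 18 refer to 8.5.1 for both collection and follow-up, which leans towards 8.5.1. None of these places says that the related-only limit overrides 12.3 for SAEs.

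**Step 3: where does the conflict stop?** Vary one feature of the test case at a time.

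- Event judged related: 8.5.1 and 12.3 both require a report. No conflict.
- Event during treatment: the 8.5.1 limit does not apply. No conflict.
- Event after new antineoplastic therapy: 8.5.1 stops AE collection, with continued assessment of related or possibly related SAEs only on the sponsor-investigator's guidance. Section 12.3 still has no end. This is a second disagreement, about when collection closes.

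**Step 4: is the threshold for related defined?** Not in 8.5.1. It uses related in one sentence and related or possibly related in another, while 12.2 records attribution on a five-level scale. Sites that adopt the limit could still draw the line in different places.

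**Step 5: is the window pharmacologically relevant?** Section 1.6.2 gives a ficlatuzumab half-life of 7 to 10 days. Day 30 is therefore 30/10 = 3 to 30/7 = 4.3 half-lives after the last dose. Attribution in this window is a real judgement, not a formality.

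**The case against.** The strongest answer is that 8.5.1 is the specific rule for the post-treatment period and expressly addresses SAEs. Sections 8.5.2, 8.5.3, 12.2 and 12.3 and the study calendar footnotes all point to it. On that reading all SAEs are reported during treatment and only related new ones afterwards, and the sections fit together. A related-only limit after treatment would then be a deliberate choice.

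This reading is possible, and it is why one cannot say that events will be captured inconsistently. It does not settle the matter, because the reporting sentence in 12.3 is unqualified and follows the deferral.

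Three stronger readings are tempting but lack support:

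- **A count of affected events.** A reader might turn the median survival of less than 6 months in Section 1.1 into an expected number of deaths within 60 days. That figure describes survival after failure of platinum, cetuximab and anti-PD1 therapy, not survival after the last study dose. Deaths are also not the same as SAEs handled differently, and new therapy can close the window early.
- **Hidden safety signals.** Nothing in the documents shows that sites misattribute events systematically. Deaths are in any case found through survival follow-up every 12 weeks (Section 8.5.3), though not as 24-hour SAE reports.
- **A 60-day duty under 12.3.** The 60 days come only from 8.5.1; Section 12.3 has no end date.

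**Conclusion.** The inconsistency holds and should be corrected. For a new SAE after the last dose that the site judges unrelated, the plan contains one rule that requires nothing and another that requires a 24-hour report, and it does not say which governs. Sites may therefore capture these events differently.

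The reach is limited. Safety review by the sponsor and DSMB and the toxicity tabulation are exposed; PFS and OS are not, because progression and survival are collected separately. Toxicity is reported descriptively in a non-comparative design (Sections 10.1 and 10.6), so no hypothesis test depends on it.

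The number of affected events cannot be derived from the documents. For scale only: with 33 evaluable patients per arm, taken from the target in Section 10.3, each patient whose only qualifying event falls in this class moves an arm's proportion by 1/33, or about 3 percentage points.

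The conclusion rests on the text alone. A lab manual, charter or site instruction outside these documents might already fix the rule.

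**What to change.** Reconcile Sections 8.5.1, 12.2 and 12.3 so that one rule states:

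1. whether attribution limits SAE reporting and database entry after the last dose;
2. when SAE collection ends, for example at 60 days or earlier at new antineoplastic therapy, with the same end stated in 12.3 and used for the toxicity analysis in 10.4.1;
3. which levels of the attribution scale count as related, wherever a related-only limit is kept.

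Either direction would remove the contradiction. Keeping the 12.3 rule for all SAEs and confining the related-only limit in 8.5.1 to non-serious AEs has one advantage: serious events would not be filtered on open-label site attribution. Section 12.2 would then need matching wording for non-serious Grade 3 or higher events after the last dose.

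The cost is a few sentences and, in that direction, some additional SAE reports for events due to the disease.

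Timing matters. Sections 5.1 and 5.4.1 end ficlatuzumab dosing by March 31, 2021, and the page footers date this version 05/23/2023. If post-treatment safety follow-up is already complete, new wording will not recover missing events. The sponsor should then establish which rule each site applied and state it with the toxicity tables.
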